4.7.1.3 Exposure Analysis

- The number of patients completing each cycle will be summarized and listed. A patient is considered to have completed a cycle for MOR00208 if he/she was compliant for all MOR00208 infusions during the cycle. A patient is considered to have completed a cycle for idelalisib or venetoclax if he/she was compliant for idelalisib or venetoclax administration during the cycle.
- Duration of exposure will be calculated for the following categories: Week (1-2], (2-4], (4-6], (6-8], etc. Summaries (i.e., mean, standard deviation, etc.) will be displayed in weeks.
- Number of infusions with MOR00208 will be summarized.

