3.10 Sample Size

The primary endpoint of this study is the incidence and severity of AEs in Cohort A (MOR00208 combined with idelalisib) and Cohort B (MOR00208 combined with venetoclax) and will be analyzed

descriptively. In each cohort approximately 12 patients will be enrolled. No formal sample size calculation was performed and no formal statistical hypothesis testing is planned.

4 Statistical Methodology

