4.3 Disposition of Patients

The number of patients screened, the number (%) of screen failures and the number of patients with each reason for screen failure will be presented (by cohort). All patients will be included.

The following summaries will be provided by cohort based on the total number of enrolled patients:

- An overview table will be provided by cohort and will include the number of patients enrolled, the number (%) of patients in each analysis set (FAS, PPS, SAF, PKAS and IAS).
- Number (%) of patients who were treated with study drug (split by MOR00208, idelalisib/venetoclax, and treated with both drugs).
- Number (%) of patients who were enrolled but not treated with study drug (split by MOR00208 and idelalisib/venetoclax).
- Number (%) of patients who discontinued treatment including the reason for discontinuation.
- Number (%) of patients who are still on any treatment (only for the primary analysis). The median time on study will be reported for patients in the FAS, which is defined as follows: $[(\text{Date of Death/last Visit including the End of Treatment Visit}) - (\text{Date of first dosing with any study drug}) + 1] / 30.4375$.

The median time on study will be derived using Kaplan-Meier-Methodology. Patients still on study at data cut-off will be censored.

The individual time on study will be graphically illustrated by a 'Swimmers Plot'. The graph will indicate the point in time the best response is reached, the best response (complete response vs. partial response), the number of prior treatment lines, and the reason for BTK inhibitor discontinuation in the last BTK inhibitor containing line. Moreover, the point in time MRD negativity is reached will be shown (see Section 4.9.3). For MRD negativity it will be differentiated between blood and bone marrow assessments, i.e., it will be indicated in the 'Swimmers Plot' when MRD negativity is reached as assessed in blood vs. bone marrow.

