4.7.1.1 Duration of Exposure to Each Individual Study Drug

Duration of exposure to an individual study drug (days) = (last date of exposure to study drug) – (date of first administration of study drug) + 1.

Taking into account the period of rest between infusions, the **last date of exposure** is defined as follows:

- For MOR00208: When the study drug is administered over several regular doses with regular time intervals, the last date of exposure is identified according to the planned dose schedule of the cycle. If no rest period is included in the cycle then the last date of exposure is: (last date of administration of the study drug) + (length of time interval-1). **Length of time interval:** 7 days in Cycle 1-3 and 14 days in Cycle 4-6 a, and 28 days from Cycle 7 onwards.
- For idelalisib and venetoclax, the last date of exposure will be defined as the last date of administration.
- For idelalisib and venetoclax, temporary dose interruptions will not be considered for calculation.

4.7.1.2 Duration of Exposure to Combination Treatment (i.e., the combination of *both* MOR00208 and idelalisib/venetoclax at the same time)

Duration of exposure to combination treatment (days) = (last date of exposure to both MOR00208 and idelalisib/venetoclax) – (date of first administration of study treatment) + 1.

The last date of exposure for each individual drug is specified in *Section 4.7.1.1*.

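### The exposure categories in SAP 4.7.1.3 have no row for 1 week or less, and SAP 4.7.1.1 lets MOR00208 exposure run past death or data cut-off by up to 6, 13 or 27 days

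*SAP*

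**What the plan says.** SAP 4.7.1.1 defines the duration for a single drug as "last date of exposure to study drug) – (date of first administration of study drug) + 1", in days. For MOR00208 the last date of exposure is "last date of administration of the study drug) + (length of time interval-1", where the interval is "7 days in Cycle 1-3 and 14 days in Cycle 4-6 a, and 28 days from Cycle 7 onwards". For the oral drugs the rule is: "For idelalisib and venetoclax, the last date of exposure will be defined as the last date of administration".

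SAP 4.7.1.3 then sets the reporting: "Duration of exposure will be calculated for the following categories: Week (1-2], (2-4], (4-6], (6-8], etc". It adds: "Summaries (i.e., mean, standard deviation, etc.) will be displayed in weeks". The same section asks for the number of MOR00208 infusions and the number of patients completing each cycle.

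Neither section mentions death or data cut-off. The SAP does have a cut-off rule in 4.3, but it applies to time on study: "Patients still on study at data cut-off will be censored". On size, SAP 3.10 says: "In each cohort approximately 12 patients will be enrolled".

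**The concern.** There are two separate gaps in the exposure rules.

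First, the lowest category is open at 1 week, so it leaves out durations of 1 to 7 days. The SAP expects such patients. Its section on cohorts (SAP section 2) uses as its example a Cohort B patient who leaves after a single MOR00208 dose and before any venetoclax, and it creates a safety column for that case. The exposure categories cannot place the same patient. In a safety run-in of about 12 patients per cohort, a frequency table that does not add up to N is conspicuous, and the programmer would have to decide unguided how to repair it.

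Second, extending MOR00208 exposure to the end of the dosing interval is a reasonable convention while the patient is alive and under observation. Without a limit, it credits exposure after death. It also credits exposure after the data cut-off to patients still on treatment. SAP 4.3 plans to count patients still on treatment at the primary analysis, so the cut-off case is foreseen.

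**Working it through.** The plan states no exposure figure to reproduce, so the check applies its rules directly. Assumptions: first MOR00208 dose on study day 1, later doses on their nominal days, weeks = days / 7.

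**Inputs.** Interval of 7 days in Cycles 1-3, 14 days in Cycles 4-6 and 28 days from Cycle 7 (SAP 4.7.1.1). Categories (1-2], (2-4], (4-6] and so on (SAP 4.7.1.3). Cycles of 28 days, venetoclax starting on Cycle 1 Day 8, about 12 patients per cohort.

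**Formula for MOR00208.** Duration = (last infusion day + interval - 1) - 1 + 1 = last infusion day + interval - 1.

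**Part 1: which durations have no category**

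| Case | Duration | Weeks | Category |
|---|---|---|---|
| MOR00208, Day 1 only | 1 + 6 = 7 days | 1.00 | none |
| MOR00208, Days 1 and 4 | 4 + 6 = 10 days | 1.43 | (1-2] |
| MOR00208, through Day 8 | 8 + 6 = 14 days | 2.00 | (1-2] |
| Oral drug stopped on its day 1 to 7 | 1 to 7 days | 0.14 to 1.00 | none |
| Oral drug stopped on its day 8 | 8 days | 1.14 | (1-2] |

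For MOR00208 the gap catches only single-infusion patients. For the oral drugs it catches any stop within 7 days of the first dose. For venetoclax that is the whole 20 mg week, study days 8 to 14. One uncategorised patient in 12 is 1/12 = 8.3%.

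**Part 2: overrun past death or cut-off**

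The overrun is largest when death or cut-off falls on the infusion day, and then equals interval - 1:

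- Cycles 1-3: 7 - 1 = 6 days
- Cycles 4-6: 14 - 1 = 13 days
- Cycle 7 onwards: 28 - 1 = 27 days

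Relative size, with death or cut-off on the infusion day:

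- Cycle 7 Day 1 is study day 6 × 28 + 1 = 169. Uncapped exposure is 169 + 27 = 196 days, capped is 169, and 27/169 = 16.0%.
- Cycle 24 Day 1 is study day 23 × 28 + 1 = 645. Uncapped exposure is 672 days, capped is 645, and 27/645 = 4.2%.

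**Comparison with time on study (SAP 4.3).** A patient who dies 2 days after Cycle 7 Day 1 has 171 days on study but 196 days of MOR00208 exposure, which is 25 days more than the time on study.

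**When the cut-off case arises.** It arises at the primary analysis for patients still on MOR00208. The final analysis is set at 5 years or about 30 days after the last patient's last treatment, whichever comes first. The largest extension is 27 days, so under the 30-day rule exposure would not pass the cut-off. It could do so only if the 5-year limit applied while patients were still being dosed.

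**The case against.** The strongest reply is that little is lost in practice, and much of it stands.

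- A reader might infer that early stops disappear from the report. They do not. They still enter the means and standard deviations, the infusion counts, the disposition table with reasons, the swimmers plot, the tables of adverse events leading to discontinuation and the drug administration listings. Only the category rows miss them.
- The first interval may be a notation slip. Every later category is two weeks wide, so the intended one could be weeks 1 and 2, that is (0-2]. This is plausible, but the text as written still excludes 1 week and below, and a one-character correction is needed.
- A reader might infer that MOR00208 and the oral drugs are measured by different rules. They are not. Last administration plus interval minus 1, with a 1-day interval, is simply the last administration date. The extension itself is deliberate and consistent; only the missing limit is at fault.
- A reader might infer that the primary endpoint is distorted. SAP 4.10.1 reports numbers of events and numbers and percentages of patients, with no person-time denominator. The treatment-emergent window runs to 30 days after the last administration, not from the last date of exposure. Neither gap changes it.
- The 27 days are a maximum and apply from Cycle 7 only. Death has to fall inside the last dosing interval, and the cut-off case mainly concerns the primary analysis.

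What remains is that both rules, followed literally, give wrong entries in the exposure tables.

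**Conclusion.** Both gaps are real and modest. The categories in SAP 4.7.1.3 do not cover durations of 1 to 7 days, so their counts will not sum to N if any patient has a single MOR00208 infusion or stops an oral drug within a week of starting it. How many patients that will be is unknown beforehand.

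The MOR00208 rule in SAP 4.7.1.1 can overstate exposure by at most 6, 13 or 27 days depending on the cycle, for patients who die or reach the cut-off within a dosing interval. The percentages (16% and 4%) take the worst case, with the event on the infusion day and nominal dosing days.

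Idelalisib and venetoclax durations do not overrun. Combination exposure (SAP 4.7.1.2) would overrun only if its last date of exposure to both drugs were not read as the earlier of the two dates, which the wording leaves open.

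This is a defect in descriptive exposure reporting. The documents do not support a claim that it hides early stops, alters adverse event incidence or affects any test. It still merits correction, because stated rules produce wrong figures and the repair is short.

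**What to change.** In SAP 4.7.1.3, make the first category cover every duration from day 1: either (0-1] followed by (1-2], or a single (0-2]. The first option shows first-week stops separately; the second keeps the two-week width. Either closes the gap.

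In SAP 4.7.1.1, define the last date of MOR00208 exposure as the earliest of (a) last infusion + interval - 1, (b) date of death and (c) data cut-off date. The overrun then becomes 0 days.

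The cost is two lines of SAP wording. No new data are needed, and dosing and follow-up do not change. Reported MOR00208 exposure becomes slightly shorter for the patients concerned.

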4.7.2 Dose Reduction

Dose reductions are only possible for venetoclax and idelalisib, but not for MOR00208. The number (%) of patients with any (i.e., permanent and transient) dose reduction will be summarized. For idelalisib, the number (%) of patients with a permanent reduction to 100 mg BID will be summarized. For venetoclax, the number of patient with a *permanent* reduction to 300 mg, 200 mg, or 100 mg will

be summarized. Moreover, the number (%) of patients who underwent no permanent reduction at all will be shown per cohort.

4.7.3 Dose Interruption

The number (%) of patients with temporary interruptions and the associated reasons will be summarized for both study drugs split by cohort.

4.7.4 Treatment Compliance

If the ratio (total used dose)/(total planned dose) is between 80% (exclusive) and 120% (inclusive) of the assigned dosage during a particular Cycle, then the patient is considered compliant for treatment.

The planned dose and the used dose will be calculated based on information collected on the eCRF pages '*Idelalisib Dosing Record*' or '*Venetoclax Dosing Record*'. As patients may change the daily dose, or transiently interrupt treatment, information on dosing will be represented differently in the eCRF for different situations:

- Patients who changed the Actual Total Daily Dose have **two (or more)** eCRF log lines for a particular Cycle or treatment period (during venetoclax ramp-up), i.e., one separate log line for each particular Actual Total Daily Dose. Each eCRF log line will contain information on the number of tablets dispensed, and the number of tablets returned.
- Patients who interrupted treatment and re-initiated treatment in the same_Cycle (or same treatment phase during ramp-up) have **two (or more)** eCRF log lines. The Actual Total Daily Dose in each log line will be identical. All eCRF log lines will contain the information on the number of tablets dispensed, and the last log line will contain the information on the number of tablets returned.
- Patients who interrupted treatment, and only re-initiated treatment at the beginning of the next Cycle or next treatment period (during venetoclax ramp-up) will have **one** eCRF log line containing all information on Actual Total Daily Dose, number of tablets dispensed, and number of tablets returned.
- Compliant patients will display only one eCRF log line for a particular cycle, or treatment phase.

The number of days on treatment for a particular Actual Total Daily Dose (represented by an individual eCRF log line) is calculated as follows:

$(\text{Dosing Stop Date} - \text{Dosing Start Date}) + 1$.

The number of days on treatment will be derived for every single eCRF log line.

Idelalisib

Idelalisib is dispensed in 28-day Cycles. The administration is bi-daily (100 mg BID or 150 mg BID). Compliance will be calculated based on the total planned dose, and the total dose actually used.

- The total ***planned*** dose per Cycle can be calculated as follows:
 - **For Cycles with one eCRF log line:**
Actual Total Daily Dose as entered in the eCRF [mg] x Number of days on treatment.
 - **For Cycles with two or more eCRF log lines (two log lines in case of one dose change, or treatment interruption with re-initiation in the same Cycle):**
E.g., for two log lines:
(Actual Total Daily Dose as entered in the eCRF [mg] in log line 1 x Number of days on treatment in log line 1) + (Actual Total Daily Dose as entered in the eCRF [mg] in log line 2) x (Number of days on treatment in log line 2).

Note: Actual Total Daily Dose may be identical for different log lines (in case of interruption), or different in case of dose change.

- The total dose ***used*** per Cycle can be derived as follows:
 - **For Cycles with one eCRF log line:**
(Actual Total Daily Dose as entered in the eCRF [mg] / 2) x (Number of tablets dispensed – Number of tablets returned).
 - **For Cycles with two or more eCRF log lines:**
 - ❖ **All log lines contain information on the number of tablets dispensed, and number of tablets returned (in case of dose change):**
E.g., for two log lines:
[(Actual Total Daily Dose as entered in the eCRF [mg] in log line 1 / 2) x (Number of tablets dispensed in log line 1 – Number of tablets returned in log line 1)] + [(Actual Total Daily Dose as entered in the eCRF [mg] in log line 2 / 2) x (Number of tablets dispensed in log line 2 – Number of tablets returned in log line 2)].
 - ❖ **All log lines for a particular Cycle contain the information on the number of tablets dispensed, and only the last log line for a particular Cycle contains number of tablets returned (in case of treatment interruption and re-initiation of treatment in the same Cycle):**
E.g., for two log lines:
[(Actual Total Daily Dose as entered in the eCRF [mg] in log line 1 / 2) x (Number of tablets dispensed in log line 1)] - [(Actual Total Daily Dose as entered in the eCRF [mg] in log line 2 / 2) x (Number of tablets returned in log line 2)].

- Calculation of compliance for a particular Cycle (%):

(sum of total dose *used* for all log lines pertaining to a particular Cycle) / (sum of total *planned* dose for all log lines pertaining to a particular Cycle) * 100.

Venetoclax

The planned daily doses of venetoclax in the ramp-up phase and beyond are as follows:

- 20 mg 1st week (study days 8 to 14)
- 50 mg 2nd week (study days 15 to 21)
- 100 mg 3rd week (study days 22 to 28)
- 200 mg 4th week (study days 29 to 35)
- 400 mg 5th week and thereafter (study days 36 and above)

Different tablet strengths are being used to target a particular Actual Total Daily Dose:

- 20 mg daily: 2 x 10 mg tablet (i.e., 14 tablets for 7 days)
- 50 mg daily: 1 x 50 mg tablet (i.e., 7 tablets for 7 days)
- 100 mg daily: 1 x 100 mg tablet (i.e., 7 tablets for 7 days)
- 200 mg daily: 2 x 100 mg tablet (i.e., 14 tablets for 7 days)
- 300 mg daily: 3 x 100 mg tablet (i.e., 84 tablets for 28 days)
- 400 mg daily: 4 x 100 mg tablet (i.e., 112 tablets for 28 days, or 84 tablets for 21 days)

For an Actual Total Daily Dose beyond 100 mg, only tablets of strength 100 mg are being administered. That is, depending on the Actual Total Daily Dose, multiples of these tablets of strength 100 mg are used for treatment.

The fact that different tablet strengths are used to target a particular Actual Total Daily Dose requires a correction factor (named Factor X) to derive the correct total dose used (see below):

- Factor X = 1: for log lines with an Actual Total Daily Dose of 50 mg or 100 mg.
- Factor X = 2: for log lines with an Actual Total Daily Dose of 20 mg or 200 mg.
- Factor X = 3: for log lines with an Actual Total Daily Dose of 300 mg.
- Factor X = 4: for log lines with an Actual Total Daily Dose of 400 mg.

Venetoclax is dispensed weekly during ramp-up, or in 28 days Cycles after ramp-up. Compliance will be calculated on the basis of the *planned* dose and actual total dose *used* per Cycle.

- The total ***planned*** dose for a particular treatment period (e.g., one week treatment with a particular dose during ramp up) can be calculated as follows:
 - **For patients and Cycles with one eCRF log line:**
Actual Total Daily Dose as entered in the eCRF [mg] x Number of days on treatment.
 - **For patients and Cycles with two or more eCRF log lines (e.g., two log lines in case of one dose change, or treatment interruption with re-initiation in the same Cycle):**
E.g., for two log lines:
[(Actual Total Daily Dose as entered in the eCRF [mg] in log line 1) x (Number of days on treatment in log line 1)] + [(Actual Total Daily Dose as entered in the eCRF [mg] in log line 2) x (Number of days on treatment in log line 2)].

Note: Actual Total Daily Dose may be identical for different log lines (in case of interruption), or different in case of dose change.
- The total dose ***used*** per Cycle can be derived as follows:
 - **For patients and Cycles with one eCRF log line:**
(Actual Total Daily Dose as entered in the eCRF [mg] / Factor X) x (Number of tablets dispensed – Number of tablets returned).
 - **For patients and Cycles with two or more eCRF log lines:**
 - ❖ **All log lines contain information on the number of tablets dispensed, and number of tablets returned (in case of dose change):**
[(Actual Total Daily Dose as entered in the eCRF [mg] in log line 1 / Factor X) x (Number of tablets dispensed in log line 1 – Number of tablets returned in log line 1)] + [(Actual Total Daily Dose as entered in the eCRF [mg] in log line 2 / Factor X) x (Number of tablets dispensed in log line 2 – Number of tablets returned in log line 2)].
 - ❖ **All log lines for a particular Cycle contain the information on the number of tablets dispensed, and only the last log line for a particular Cycle contains the information on number of tablets returned (in case of treatment interruption and re-initiation of treatment in the same Cycle):**
[(Actual Total Daily Dose as entered in the eCRF [mg] in log line 1 / Factor X) x (Number of tablets dispensed in log line 1) - [(Actual Total Daily Dose as entered in the eCRF [mg] in log line 2 / Factor X) x (Number of tablets returned in log line 2)].
- Calculation of compliance for a particular Cycle (%):
(sum of total dose ***used*** for all log lines pertaining to a particular Cycle) / (sum of total ***planned*** dose for all log lines pertaining to a particular Cycle) * 100.

MOR00208

A patient will be considered compliant with the protocol if the MOR00208 dose administered is >80% and ≤120% of the planned dosage per single infusion. Therefore MOR00208 compliance will be presented for each infusion.

Furthermore, MOR00208 dosage will be summarized by cycle as well. The total administered dose per cycle will be divided by the total planned dose per cycle. One MOR00208 dose can be missed between Cycles 1-3, between Cycles 4-12 and one dose between Cycles 13-24 without the patient being non-compliant (skipped doses of MOR00208 due to toxicity will not be considered for calculation of compliance).

A summary displaying the number and percentage of patients in the following categories will also be presented for each study drug, and each cycle:

- ≤80%
- >80 – 120%
- >120%

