8.12 Treatment Accountability and Compliance

The pharmacist or other designated individual will maintain records of study treatment delivered to the study site; the inventory at the site; the distribution to and use by each patient; and the return of materials to the sponsor or disposal. These records should include dates, quantities, batch/serial numbers, expiration dates, in-clinic temperature log, and unique code numbers assigned to the product and study patients.

Patients will receive MOR00208 under the direct supervision of study personnel. Each administration volume or dose will be checked and the vial/outer package code and volume or dose per administration will be recorded in each patient's eCRF as well as in the source data.

At each visit after initiation of treatment, site staff will record compliance of patients with their assigned regimen. Patients will be instructed to bring unused/partially used/empty medication containers of idelalisib or venetoclax back for inspection on Day 1 of each cycle, starting with Cycle 2, or on the EOT visit as compliance will be assessed by tablet counts.

Patients are to be reminded of the importance of compliance with their assigned regimen, with an emphasis on taking their study drug on schedule, and maintaining the prescribed interval between doses.

Investigators will maintain records that document adequately that the patients were provided with the correct study treatment kits and will reconcile the products received from the drug dispensing center. Drug accountability will be checked by the field monitor during site visits and at the completion of the trial.

Noncompliance in general is defined as taking $\leq 80\%$ or $>120\%$ of one MOR00208 dose and/or $\leq 80\%$ or $>120\%$ of the idelalisib or venetoclax intake per cycle during any outpatient evaluation period.

Moreover, one MOR00208 dose can be missed between Cycles 1 and 3, between Cycles 4 and

12 and one dose between Cycles 13 and 24 without the patient being non-compliant. Note that MOR00208 dose omissions due to toxicity are covered in Sections 8.6 and 8.9.

Discontinuation for noncompliance is at the Investigator's discretion and is to be noted on the eCRF.

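### Oral-drug compliance is measured against the dose on dosing days only, so a cycle dosed on 3 of 28 days can score 100% and be tabulated as completed

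*SAP*

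**What the plan says.** SAP 4.7.4 calls a patient compliant if the ratio of total used to total planned dose "is between 80% (exclusive) and 120% (inclusive) of the assigned dosage during a particular Cycle". For one dosing-record line, the planned dose of either oral drug is "Actual Total Daily Dose as entered in the eCRF [mg] x Number of days on treatment". With several lines, the products are summed. Days are stop date minus start date plus 1, and "The number of days on treatment will be derived for every single eCRF log line". The used dose comes from tablets dispensed minus tablets returned.

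The same section describes how interruptions are recorded. An interruption with restart in the same cycle gives two or more lines. One that lasts to the next cycle gives a single line. A dose change opens a line at the new dose. The section also lists the scheduled venetoclax dose by study day, but the planned-dose formula does not use that list.

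Two other sections bear on this:

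- SAP 4.7.1.3: "A patient is considered to have completed a cycle for idelalisib or venetoclax if he/she was compliant for idelalisib or venetoclax administration during the cycle".
- SAP 4.7.1.1, on exposure duration: "For idelalisib and venetoclax, temporary dose interruptions will not be considered for calculation".

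For MOR00208, SAP 4.7.4 states that "skipped doses of MOR00208 due to toxicity will not be considered for calculation of compliance". SAP 4.7.1.3 does summarise the number of MOR00208 infusions. Protocol 8.12 sets the same 80% and 120% limits for oral intake per cycle, assessed by tablet count, without defining the denominator.

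**The concern.** The word *planned* suggests a comparison with the protocol schedule. The formula instead compares tablets taken with the dose in force on the days the drug was open in the dosing record. A recorded interruption removes its days from both sides of the ratio, and a reduction lowers both sides equally. As an adherence measure this can be defended. As the definition of a completed cycle it gives the wrong answer, because a cycle can be almost wholly undelivered and still count as completed.

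The situation is foreseeable. Protocol 8.7 to 8.10 direct withholding of the oral drugs for many toxicities, and Protocol 8.11 provides for interruptions of up to 28 days, the length of a cycle. Safety is the primary objective, and readers will look at Tables 14.3.7.5.1 and 14.3.7.5.2 (Exposure and Treatment Compliance) to learn how much treatment lay behind the adverse events. With about 12 patients per cohort, one misclassified patient moves a completion percentage by 1/12 = 8.3 points.

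**Working it through.** **Inputs.** Idelalisib is scheduled at 150 mg twice daily = 300 mg/day (Protocol 8.1.2), with 100 mg twice daily = 200 mg/day as the reduced dose (Protocol 8.7). Venetoclax is scheduled at 400 mg/day after ramp-up (Protocol 8.1.3), and Table 6 of the Protocol includes 300 mg as a reduced dose. A cycle is 28 days. Formulas are those of SAP 4.7.4:

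- planned = sum over lines of (actual daily dose × days on that line)
- used = (actual daily dose / 2 for idelalisib, or / Factor X for venetoclax) × (dispensed − returned)
- compliance = used / planned × 100

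**Step 1: the SAP's own figures.** At 400 mg/day for 28 days, Factor X = 4 gives 4 × 28 = 112 tablets, as the SAP states. Used = 400/4 × 112 = 11,200 mg and planned = 400 × 28 = 11,200 mg, so compliance is 100%. All seven venetoclax tablet counts in SAP 4.7.4 reproduce in this way, each at 100%.

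**Step 2: recorded interruptions and reductions.** The last column divides dose used by the scheduled dose over 28 days (idelalisib 300 × 28 = 8,400 mg; venetoclax 400 × 28 = 11,200 mg).

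| Cycle | Used / planned (mg) | SAP ratio | Share of schedule |
|---|---|---|---|
| Idelalisib 300 mg/day for 3 days, then withheld | 900 / 900 | 100% | 900/8,400 = 10.7% |
| Idelalisib 200 mg/day for 28 days | 5,600 / 5,600 | 100% | 5,600/8,400 = 66.7% |
| Venetoclax 400 mg/day for 5 days, then withheld | 2,000 / 2,000 | 100% | 2,000/11,200 = 17.9% |
| Venetoclax 300 mg/day for 28 days | 8,400 / 8,400 | 100% | 8,400/11,200 = 75.0% |

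Under SAP 4.7.1.3 all four cycles are completed. For the second and fourth, that is reasonable. For the first and third, it is not.

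**Step 3: restart within the cycle.** Take 3 idelalisib days split as 2 + 1, with 60 tablets dispensed (one bottle, an assumption that does not affect the ratio) and 54 returned. Planned = 300 × 2 + 300 × 1 = 900 mg. Used = 150 × 60 − 150 × 54 = 900 mg. Compliance is again 100%.

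**Step 4: what the ratio does detect.** If the same 6 tablets are taken but the line stays open to Day 28, planned = 300 × 28 = 8,400 mg and compliance = 900/8,400 = 10.7%. Missed tablets inside an open line are found; time off drug with a recorded stop date is not.

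**Step 5: empty cycles.** With no dosing days the ratio is 0/0, and the SAP gives no rule.

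**The case against.** The strongest reply is that compliance means following the assigned regimen. Protocol 8.12 uses that concept and SAP 4.7.4 refers to the assigned dosage. A patient who obeys a directed hold or reduction is compliant, and a ratio that left this out would penalise correct conduct. This stands for the ratio itself. It does not rescue the label *planned* or the use of the ratio to define completion. The oral formula also drops every recorded interruption whatever its reason, whereas the MOR00208 rule drops only doses skipped for toxicity.

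A reader might go further and infer that interruptions and reductions disappear from the report, that tolerability is therefore overstated, and that AE rates and ORR are distorted. The documents do not support this:

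- SAP 4.7.2 counts patients with reductions, including permanent ones by dose level, and SAP 4.7.3 counts interruptions with reasons.
- SAP 4.10.1.7.1 tabulates adverse events leading to any action, discontinuation or interruption, split by drug.
- Listings 16.2.5.1.1 to 16.2.5.1.3 show the administration records, and the MOR00208 infusion count falls with each omitted infusion.
- AE incidence and ORR are proportions of patients, not divided by exposure, and no hypothesis is tested.

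A reader might also infer that completion should require more than 80% of the full scheduled dose. That would fail every fully taken cycle at a permitted reduced dose (66.7% and 75.0% above). It would also score 0% for responders with marrow MRD negativity who stop the oral drug as Protocol 9.2.7 and SAP 3.3.1 allow.

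**Conclusion.** The point holds in a limited form. As SAP 4.7.4 and 4.7.1.3 are written, recorded oral-drug interruptions and reductions do not lower compliance, and a patient dosed on 3 of 28 days scores 100% and has completed the cycle at 10.7% of the scheduled dose. This assumes that the interruption is recorded with a stop date, as the SAP describes, and that tablets on dosing days were taken. The examples show what the rule does; the documents give no expected frequency of such cycles.

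Interruptions and reductions remain visible as patient counts and in listings. What no planned oral-drug summary gives is the amount of dose or the number of days lost. Because these are descriptive exposure tables that feed no endpoint, analysis set or stated decision rule, the change should be made but is not critical to the validity of the trial's results.

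**What to change.** 1. **SAP 4.7.4, label.** Keep the ratio and call it adherence to prescribed dose on dosing days.
2. **SAP 4.7.4, addition.** Add a descriptive relative dose delivery per cycle and drug: dose used divided by scheduled dose over the scheduled days.
   - Idelalisib: 8,400 mg per cycle.
   - Venetoclax, from the SAP's own schedule: 7 × (20 + 50 + 100) = 1,190 mg in Cycle 1, 7 × 200 + 21 × 400 = 9,800 mg in Cycle 2, and 11,200 mg thereafter.
   - MOR00208: all scheduled infusions, including those skipped for toxicity.
   - Show cycles after a permitted oral-drug stop for response separately, and state a rule for cycles with no dosing days.
3. **SAP 4.7.1.3.** Define oral-drug completion on days dosed out of scheduled cycle days, for example more than 80%, together with adherence. Over 28 days this needs 23 days (82.1%; 22 days is 78.6%). The 3-day cycle fails, and a full cycle at a permitted reduced dose still counts.
4. **SAP 4.7.1.1.** Report days on drug net of interruptions beside the elapsed duration.

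The cost is SAP wording and a little more programming. Doses, dates, tablet counts and infusions are already recorded, and nothing in trial conduct changes. The downside is that delivery and completion figures may look less favourable. The change should be settled before database lock.
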